## 4.3. Justification for Dose

The planned dose of 500 mg IV Q2W for patients with CSU was chosen based on an analysis with preliminary human PK and receptor occupancy data from healthy subjects who received single (1 to 1000 mg) or repeat (200 mg x 2 doses) IV doses of LY3454738 in the Phase 1 Study FRCC. Based on the preliminary analysis, the half-life of LY3454738 is approximately 2 weeks, and a Q2W dose of 500 mg is expected to achieve approximately 90% saturation of the receptor at the trough drug concentration at steady state ( $C_{min,ss}$ ). Receptor occupancy is used as a surrogate of pharmacological activity, and receptor saturation is desired to maximize the probability of achieving clinical efficacy.

This 500 mg IV Q2W dose was predicted to achieve a steady-state exposure that is similar to the maximum exposure achieved after the highest dose tested as a single dose in Study FRCC (that is, 1000 mg). In the single-ascending dose portion of Study FRCC, there were no dose-limiting safety findings. See the IB for additional information.

Dose selection is further supported by preclinical toxicity data. LY3454738 was evaluated in cynomolgus monkeys over a 3-month dosing period, during which LY3454738 was administered once weekly at doses of 0, 15, or 50 mg/kg subcutaneous or 170 mg/kg IV (13 total doses). The no-observed-adverse-effect level (NOAEL) in this study was 170 mg/kg, and this provides a margin of safety of  $\geq$ 33-fold (based on mg/kg dose or estimated human exposure) to a repeated dose of 500 mg Q2W. See the IB for additional information supportive of the dose selection.

## 4.4. End-of-Study Definition

A participant is considered to have completed the study if he or she has completed all required phases of the study including the last visit or the last scheduled procedure shown in the SoA (Section 1.3).

The end of the study is defined as the date of the last visit or last scheduled procedure shown in the SoA (Section 1.3) for the last participant in the trial globally.

### 5. Study Population

Prospective approval of protocol deviations to recruitment and enrollment criteria, also known as protocol waivers or exemptions, is not permitted.

All screening evaluations must be completed and reviewed to confirm that potential participants meet all eligibility criteria.

The investigator will maintain a screening log to record details of all participants screened and to confirm eligibility or record reasons for screening failure, as applicable.

For screen failures and rescreening activities within the screening period, see Section 5.4.

### 5.1. Inclusion Criteria

Participants are eligible to be included in the study only if they meet all of the following criteria during screening, unless otherwise specified below:

#### **Informed consent**

[1] Have provided signed informed consent as described in Appendix 10.1 and are capable of compliance with the requirements and restrictions listed in the informed consent form and in this protocol.

#### **Participant characteristics**

- [2] Are male or female participants from 18 to 65 years of age, inclusive, at the time of signing the informed consent document.
  - [2a] Female participants:

#### Women of childbearing potential (WOCBP)

Women of childbearing potential who are abstinent (if this is complete abstinence, as their preferred and usual lifestyle) or in a same-sex relationship (as part of their preferred and usual lifestyle) must agree to either remain abstinent or stay in a same-sex relationship without sexual relationships with males. Periodic abstinence (for example, calendar, ovulation, symptothermal, post-ovulation methods), declaration of abstinence just for the duration of the trial, and withdrawal are not acceptable methods of contraception.

Otherwise, WOCBP who participate in the study must agree to use two forms of effective contraception, where at least one form is highly effective (less than 1% failure rate) for the entirety of the study.

Abstinence or contraception must continue following completion of study drug administration until their plasma concentrations are below the level that could result in a relevant potential exposure to a possible fetus, predicted to be 90 days following last dose of study drug.

A. Women of childbearing potential participating must test negative for pregnancy prior to initiation of treatment as indicated by a negative serum pregnancy test at the

screening visit followed by a negative urine pregnancy test within 24 hours prior to exposure. Women must also test negative for pregnancy prior to each dose.

B. Two forms of effective contraception, where at least one form is highly effective (such as combination oral contraceptives, implanted contraceptives, or intrauterine devices) will be used. Effective contraception (such as male or female condoms with spermicide, diaphragms with spermicide or cervical sponges) may be used as the second therapy. Barrier protection methods without concomitant use of a spermicide are not a reliable or acceptable method. Thus, each barrier method must include use of a spermicide (that is, condom with spermicide, diaphragm with spermicide, female condoms as a double-barrier method is not considered acceptable due to the high failure rate when these methods are combined.

Women not of childbearing potential may participate and include those who are

- A. infertile due to surgical sterilization (hysterectomy, bilateral oophorectomy, or tubal ligation), congenital anomaly such as mullerian agenesis; or
- B. post-menopausal defined as either
  - i. A woman at least 40 years of age with an intact uterus, not on hormone therapy, who has cessation of menses for at least 1 year without an alternative medical cause and a follicle-stimulating hormone (FSH) >40 IU/mL; or
  - ii. A woman at least 55 years of age not on hormone therapy, who has had at least 12 months of spontaneous amenorrhea; or
  - iii. A woman at least 55 years of age with a diagnosis of menopause prior to starting hormone replacement therapy.

#### [2b] Male participants:

Men, regardless of their fertility status, with nonpregnant WOCBP partners must agree to either remain abstinent (if this is their preferred and usual lifestyle) or use condoms as well as one additional highly effective (less than 1% failure rate) method of contraception (such as combination oral contraceptives, implanted contraceptives, or intrauterine devices) or effective method of contraception (such as diaphragms with spermicide or cervical sponges) for the duration of the study and until their plasma concentrations are below the level that could result in a relevant potential exposure to a possible fetus, predicted to be 90 days following the last dose of study drug.

Men and their partners may choose to use a double-barrier method of contraception. Barrier protection methods without concomitant use of a spermicide are not an effective or acceptable method of contraception. Thus, each barrier method must include use of a spermicide. It should be noted, however, that the use of male and female condoms as a double-barrier method is not considered acceptable due to the high failure rate when these barrier methods are combined.

Periodic abstinence (for example, calendar, ovulation, symptothermal, post-ovulation methods), declaration of abstinence just for the duration of a trial, and withdrawal are not acceptable methods of contraception.

Men with pregnant partners should use condoms during intercourse for the duration of the study and until the end of estimated relevant potential exposure in WOCBP, predicted to be 90 days following the last dose of study drug.

Men should refrain from sperm donation for the duration of the study and until their plasma concentrations are below the level that could result in a relevant potential exposure to a possible fetus, predicted to be 90 days following the last dose of study drug.

Men who are in exclusively same-sex relationships as their preferred and usual lifestyle are not required to use contraception.

#### **CSU-related inclusion criteria**

[3] Have a diagnosis of CSU for at least 6 months before the screening visit.

Note: CSU is as defined by the 2018 revision of the EAACI/GALEN/EDF/WAO guideline for the definition, classification, diagnosis, and management of urticaria [Zuberbier et al. 2018]).

- [4] Have hives associated with itching at any time for at least 8 consecutive weeks before the baseline (randomization) visit, despite current use of H1-antihistamines.
- [5] Are taking an approved (marketed) 24-hour oral dose of a second-generation H1-antihistamine (cetirizine, levocetirizine, fexofenadine, loratadine, desloratadine, rupatadine, mizolastine, bilastine) for CSU for at least 10 consecutive days before the baseline (randomization) visit, and agree to continue taking this medication at the same dose every day throughout the study (Section 6.5.1).

Note: If the participant is not already taking this medication at the screening visit, he or she may be eligible for the study if he or she agrees to take this medication for at least 10 consecutive days before the baseline (randomization) visit, agrees to continue taking this medication every day throughout the study at same dose, and meets all other study eligibility criteria.

- [6] Are willing and able to complete the scheduled study assessments, including twice daily diary entry.
- [7] Have an urticaria activity score during a 7-day period (UAS7 score) of 16 or more during the 7 consecutive days prior to the baseline (randomization) visit.
- [8] Have no more than 5 missing diary entries for the 7 days before the baseline (randomization) visit.
- [9] If the participant's CSU symptoms are triggered or worsened by aspirin and/or nonsteroidal anti-inflammatory drugs (NSAIDs), the participant must agree not to use the triggering agent during the study.

### 5.2. Exclusion Criteria

Participants will be excluded from study enrollment if they meet any of the following criteria within the screening period.

#### Skin diseases and skin conditions other than CSU

- [10] Have a clearly defined underlying cause for chronic urticaria other than CSU. Such causes can include, but are not limited to, the following: symptomatic dermatographism (urticaria factitia); cold-, heat-, solar-, pressure-, delayed pressure-, aquagenic-, cholinergic-, or contact-urticaria.
- [11] Have diseases, other than chronic urticaria, with urticarial or angioedema symptoms. These diseases include, but are not limited to, urticarial vasculitis, urticaria pigmentosa, erythema multiforme, mastocytosis, hereditary, or acquired angioedema (for example, due to C1 inhibitor deficiency), lymphoma, leukemia, or generalized malignancy.
- [12] Have any other skin disease associated with chronic itching that, in the investigator's opinion, might influence the study evaluations and results (including, but not limited to, prurigo nodularis, atopic dermatitis, bullous pemphigoid, dermatitis herpetiformis, and senile pruritus).

#### Infections

- [13] Have a current or recent acute, active infection. For at least 30 days prior to screening, participants must have no significant symptoms including fever of 100.5°F (38°C) or above, at screening or baseline, and/or signs of confirmed or suspected infection, and must have completed any appropriate anti-infective treatment.
- [14] Have had, within 6 months of screening, any of the following types of infection:
  - Serious infections (requiring hospitalization, and/or intravenous antibiotic treatment)
  - Opportunistic infections (as defined in Winthrop et al. 2015)
  - Herpes zoster that is considered active and ongoing until all vesicles are dry and crusted over
  - Chronic infections (duration of symptoms, signs, and/or treatment of 6 weeks or longer)
  - Recurring infection (including, but not limited to, herpes simplex, herpes zoster, recurring cellulitis, chronic osteomyelitis)
    - Participants with only recurrent, mild, and uncomplicated orolabial and/or genital herpes may be discussed with the Lilly-designated medical monitor for possible exemption from this exclusion criterion.
- [15] Have human immunodeficiency virus (HIV) infection.
- [16] Have a current or past infection with hepatitis B virus (HBV) (that is, positive for hepatitis B surface antigen [HBsAg] and/or hepatitis B core antibody) (see Section 8.2.8).
- [17] Have a current infection with hepatitis C virus (HCV) (that is, positive for HCV ribonucleic acid [RNA]) (see Section 8.2.9).
- [18] Have current or past active tuberculosis (TB) (see Section 8.2.7).
- [19] Have or have had latent TB infection (LTBI) that has not been treated with a complete course of appropriate therapy as defined by the World Health Organization (WHO) and/or the United States Centers for Disease Control and Prevention (CDC), unless such treatment is underway (see Section 8.2.7).

[20] Have received a Bacillus Calmette-Guerin (BCG) vaccination or treatment within 12 months of screening, or received any other live vaccines (that is, live attenuated), within 3 months before the screening visit, or intend to receive a live vaccine (or live attenuated vaccine) during the study or within 90 days after the last dose of study drug.

Note: Use of nonlive (inactivated) vaccinations is allowed for all participants.

- [21] Have evidence of parasitic infection, defined as meeting any of the following three criteria:
  - 1) risk factors for parasitic disease (living in an endemic area, chronic gastrointestinal symptoms, travel within the last 6 months to an endemic area and/or chronic immunosuppression)
  - 2) an absolute eosinophil count >2 times the upper limit of normal (ULN)
  - 3) evidence of parasitic colonization or infection on stool evaluation for ova and parasites.

Note: Stool evaluation for ova and parasites will be conducted only in participants with risk factors (#1 above) and an eosinophil count >2 times ULN (#2 above).

#### Other medical conditions/history

- [22] Have an unstable or uncontrolled illness, including but not limited to cerebrocardiovascular (for example, unstable angina, unstable arterial hypertension, moderate-to-severe heart failure [New York Heart Association Class III/IV]), respiratory, gastrointestinal, hepatic, renal, endocrine, hematologic, or neurologic disorders that would potentially affect the participant's safety in the study or confound efficacy and safety assessments.
- [23] Have a diagnosis or history of malignancy within 5 years prior to the baseline (randomization) visit, with the following exceptions:
  - a. Basal cell or squamous epithelial carcinomas of the skin that have been resected with no evidence of metastatic disease for 3 years,
  - b. Cervical carcinoma in situ, with no evidence of recurrence within the 5 years prior to baseline (randomization) visit.
- [24] Have a history of anaphylaxis.
- [25] Have a history of chronic alcohol abuse, IV drug abuse, or other illicit drug abuse within 1 year prior to the screening visit.

Note: Marijuana is considered an illicit drug for the purposes of this study, regardless of local laws. Cannabidiol (CBD) products may be used during the study if they are derived exclusively from hemp. Participants who use hemp-based CBD products must be on a stable dose for at least 10 days prior to the baseline visit, and participants must remain on that stable dose during the study.

[26] Have a history of asthma with severity classified greater than intermittent asthma.

Note: Intermittent asthma is defined according to "Expert Panel Report 3: Guidelines for the Diagnosis and Management of Asthma Summary Report 2007 (EPR-3)" (2007 Expert Panel).

#### **Diagnostic assessments**

- [27] Have any of the following specific abnormalities on screening laboratory tests:
  - a. Serum creatinine, aspartate aminotransferase (AST), or alanine aminotransferase (ALT) ≥2 times ULN
  - b. Alkaline phosphatase (ALP)  $\geq 2$  times ULN
  - c. Total bilirubin level (TBL) ≥1.5 times ULN
  - d. Hemoglobin <10.0 g/dL (<100.0 g/L)
  - e. Total white blood cell count <2500 cells/ $\mu$ L (<2.50x10^3/ $\mu$ L or <2.50 GI/L)
  - f. Neutropenia (absolute neutrophil count <1200 cells/ $\mu$ L) (<1.20x10^3/ $\mu$ L or <1.20 GI/L)
  - g. Lymphopenia (lymphocyte count <750 cells/ $\mu$ L) (<0.75x10^3/ $\mu$ L or <0.75 GI/L)
  - h. Thrombocytopenia (platelet count <100,000 cells/µL) (<100x103/µL or <100 GI/L)

Note: For each aforementioned test, 1 repeat testing is allowed during screening, and values resulting from repeat testing may be accepted for a participant's enrollment eligibility if the other eligibility criteria are met (see Section 5.4.1).

[28] Have screening electrocardiogram (ECG) abnormalities that, in the opinion of the investigator, are clinically significant and indicate an unacceptable risk for the participant's safety in the study.

#### Prior or concomitant therapy

[29] Have used any first generation H1-antihistamine, H2-antihistamine or leukotrienereceptor antagonist within 10 days before the baseline (randomization) visit.

Note: The first generation  $H_1$ -antihistamine diphenhydramine is allowed as rescue medication before the baseline (randomization) visit per Section 6.5.2.

Note: Participants taking H2-antihistamines for gastroesophageal reflux disease (GERD) during the screening period may be eligible for the study if the other study eligibility criteria are met; such participants may continue to take this medication at a stable dose during the study.

- [30] Have received routine administration (that is, daily or every other day for 5 or more consecutive days) of systemic glucocorticoids, hydroxychloroquine, methotrexate, cyclosporine, cyclophosphamide, doxepin, or IV immunoglobulin for any indication within 30 days before the baseline (randomization) visit.
- [31] Have received prior treatment with omalizumab, ligelizumab, or any other approved or investigational biologic compound for CSU.

Note: Participants with prior use of investigational antihistamines may be eligible for the study if the other study eligibility criteria are met and if the investigational antihistamines are discontinued within 30 days or 5 half-lives, whichever is longer, before the baseline (randomization) visit.

[32] Have received within 30 days of the baseline (randomization) visit, corticosteroids (inhaled or oral), long-acting beta agonists, cromolyn, theophylline, zileuton, or monoclonal antibodies targeting interleukin-13 (IL-13), IL-4/IL-13 receptor (dupilumab), IL-5 (mepolizumab, reslizumab), or IL-5 receptor (benralizumab).

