## 4. Study Design

## 4.1. Overall Design

Study J1B-MC-FRCF (FRCF) is a multicenter, randomized, double-blind, placebo-controlled, Phase 2 crossover study to evaluate the efficacy and safety of LY3454738 500 mg given intravenously (IV) every 2 weeks (Q2W) versus placebo IV Q2W in adults with CSU inadequately controlled with H1-antihistamines.

The study duration will be up to approximately 39 weeks over 4 study periods, as shown below:

- Period 1: Screening, lasting up to 35 days before Week 0 (Visit 2, baseline)
- Period 2: First 12-week treatment, from Week 0 (Day 1) through Week 12:
  - Participants will be randomized in a 3:1 ratio to receive either LY3454738 500 mg IV or placebo IV Q2W
- Period 3: Second 12-week treatment (crossover), from Week 12 through Week 24:
  - Participants who received LY3454738 500 mg IV in Period 2 will receive placebo IV Q2W in Period 3.
  - Participants who received placebo IV in Period 2 will receive LY3454738 500 mg IV Q2W in Period 3.

Period 4: Post-treatment follow-up for approximately 10 weeks.

- Participants will not receive study drug in Period 4.
- The last dose of study drug is given at Week 22, which is 6 weeks before the first post-treatment follow-up visit (Visit 801). Thus, participants will have been withdrawn from study drug for a total of 12 weeks at the last post-treatment follow-up visit (Visit 802).

The study schema is presented in Section 1.2.

Throughout the study, participants will take a second-generation  $H_1$ -antihistamine at a dose specified in approved product labeling. Certain participants may receive rescue therapy as described in Section 6.5.2.

Participants who permanently discontinue the study drug early (Section 7.1) will undergo early termination procedures, including an early termination visit (ETV) and the post-treatment follow-up visits specified in the Schedule of Activities (SoA) (Section 1.3).

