### Allowed rescreening after failure to meet certain study eligibility criteria

An individual who has failed screening because of one or more of the following eligibility criteria may be rescreened **one time** if the reason for screen failure has resolved and if the sponsor has approved the rescreening:

[2a/B], specifically for women not of childbearing potential who are rescreening for postmenopausal status

[3], [4], [5], [7], to satisfy requirements for disease activity/duration

[13], [14], to satisfy requirements for infection-free time

[20], to satisfy requirement for timings of vaccination

[23], to satisfy requirement for cancer-free time

- [27], to address requirements for specific abnormalities on screening laboratory tests
- [29], [30], [32], [34], to satisfy medication washout periods
- [36], to satisfy requirement for timing of blood donations.

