# 6.5.4. Prohibited Concomitant Therapy

The following table lists medications that are prohibited as concomitant therapy during the study, unless an exception is noted in the "Exceptions" column. Of note, patients who have received monoclonal antibodies that target IgE (for example, omalizumab, ligelizumab) are not eligible

for study enrollment (Section 5.2), and the use of such medications during the study is prohibited.

Prohibited as Concomitant Therapy	Exceptions
Aspirin, if participant has history of CSU symptoms triggered or worsened by	Allowed if participant has no such
aspirin	history
Bacillus Calmette-Guerin (BCG) vaccine	
Cromolyn	
Cyclophosphamide	
Cyclosporine	
Doxepin	
H 2 -antihistamines (for example, ranitidine, famotidine, etc.)	Allowed for treatment of GERD
Hydroxychloroquine	
Investigational biologic for CSU	
IV immunoglobulin	
Leukotriene-receptor antagonists (for example, montelukast, zafirlukast, etc.)	
Live or live attenuated vaccine	
Long-acting beta agonists (for example, salmeterol, formoterol, etc.)	
Methotrexate	
Monoclonal antibodies targeting	
IL-13 (for example, tralokinumab)	
IL-4/IL-13 receptor (for example, dupilumab)	
IL-5 (for example, mepolizumab, reslizumab)	
IL-5 receptor (for example, benralizumab), or	
IgE (for example, omalizumab, ligelizumab)	
NSAIDs, if participant has history of CSU symptoms triggered or worsened by	Allowed if participant has no such
NSAIDs (for example, ibuprofen, naproxen, etc.)	history
Systemic corticosteroids/glucocorticoids (inhaled or oral), for example:	
beclomethasone	
budesonide	
ciclesonide	
flunisolide	
fluticasone	
mometasone	
methylprednisolone	
prednisone, etc.)	
Theophylline	
Zileuton	

Abbreviations: CSU = chronic spontaneous urticaria; GERD = gastroesophageal reflux disease; IgE = immunoglobulin E; IL = interleukin; IV = intravenous; NSAID = nonsteroidal anti-inflammatory drug.

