#### **Prohibited Concomitant Medication Use**

- The participant requires treatment with a prohibited medication (Section 6.5.4).
- The participant changes the background H1-antihistamine.

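### Exclusion [30] defines routine use by daily or alternate-day dosing, so regular methotrexate, cyclophosphamide or IV immunoglobulin at longer intervals passes entry although Section 6.5.4 prohibits these drugs on study

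*Protocol*

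**What the plan says.** Protocol Section 5.2, exclusion [30], names seven drugs or drug classes. It excludes people who have had "routine administration (that is, daily or every other day for 5 or more consecutive days) of systemic glucocorticoids, hydroxychloroquine, methotrexate", and the list continues "cyclosporine, cyclophosphamide, doxepin, or IV immunoglobulin for any indication within 30 days before the baseline (randomization) visit". The words in brackets are introduced as a definition, not an example, and they stand before the list, so they apply to every item in it.

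Section 5.4.1 shows what [30] is for. It groups the criterion with others for which rescreening is allowed: "29], [30], [32], [34], to satisfy medication washout periods".

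Section 6.5.4 governs the time on study: "The following table lists medications that are prohibited as concomitant therapy during the study, unless an exception is noted". Methotrexate, cyclophosphamide and IV immunoglobulin each have a row in that table. None has an exception, and none is limited by how often the drug is given.

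Section 7.1.1 lists, among possible reasons for permanent discontinuation of study drug: "The participant requires treatment with a prohibited medication (Section 6.5.4".

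**The concern.** One definition of routine use, built on doses given every day or every second day, is applied to drugs that may be given regularly at longer intervals. For such use the criterion provides no washout, although Section 5.4.1 treats it as a washout criterion. Section 6.5.4 then prohibits any use of the same drugs.

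Two things are at stake.

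- **The primary endpoint.** Baseline UAS7 is the score over the 7 days before first treatment (Section 8.1.1.1). If it is measured while an immunosuppressant still acts, and that drug must stop, later change mixes withdrawal with study treatment.
- **Overlap of effects.** Section 2.3 describes LY3454738 as intended to have immunosuppressive effects, so residual immunosuppression would coincide with it.

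**Working it through.** This is a comparison of texts. The plan states no figure on the point, so there is none to reproduce.

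**1. Apply the definition in [30].** Inputs from [30]: a look-back of 30 days, and dosing every day or every second day over at least 5 days. Take regular dosing every *k* days and consider every possible start day. The criterion is met if there is a run of doses no more than 2 days apart that spans at least 5 days. The number of doses in the window lies between 30/*k* rounded down and 30/*k* rounded up. For *k* of 3 or more, successive doses are always more than 2 days apart, so no run forms. The values of *k* are assumed, because the documents give no dosing intervals for these drugs.

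| Interval *k* (days) | Doses in 30 days | Meets [30]? |
|---|---|---|
| 1 | 30 | yes |
| 2 | 15 | yes |
| 3 | 10 | no |
| 7 | 4–5 | no |
| 14 | 2–3 | no |
| 21 | 1–2 | no |
| 28 | 1–2 | no |

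The answer is the same for every interval of 3 days or more. Daily oral cyclophosphamide, or IV immunoglobulin on 5 consecutive days, is caught.

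**2. Compare the neighbouring criterion.** Exclusion [32] is written without a frequency qualifier: "Have received within 30 days of the baseline (randomization) visit, corticosteroids (inhaled or oral), long-acting beta agonists". It does not list methotrexate, cyclophosphamide or IV immunoglobulin. No entry criterion other than [30] names them.

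**3. Look for another entry rule that would catch these people.**

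- Inclusion [1] requires the ability to comply with protocol restrictions. It may screen out someone who cannot stop the drug, but it sets no interval for someone who can.
- Exclusion [21] reads "Have evidence of parasitic infection, defined as meeting any of the following three criteria", and the first of the three mentions chronic immunosuppression as a risk factor. Its note and Section 8.2.5 send people with a risk factor and raised eosinophils to stool testing and allow randomization after a negative result, so a risk factor alone is not operated as an exclusion. Section 8.2.7 also provides for TB skin testing of people on immunosuppressants.
- Exclusion [22] concerns unstable or uncontrolled illness, not stable users.
- Exclusion [31] reaches biologics given for CSU. At most it touches IV immunoglobulin for that indication, whereas [30] covers any indication.

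**4. Check the timing.** Section 6.5.4 applies during the study, which may include screening. Section 4.1 gives "Period 1: Screening, lasting up to 35 days before Week 0 (Visit 2, baseline": a maximum and no minimum. Inclusion [8] allows at most 5 missing diary entries in the 7 days before baseline. With two entries a day that is 14 − 5 = 9 entries, and 9/2 = 4.5, so at least 5 diary days. The practical minimum is therefore about one week. Suppose the last dose falls on the day before consent and screening lasts 7 days. Baseline is then 8 days after that dose. On an assumed 28-day interval the next dose is not due for another 28 − 8 = 20 days. This person has broken no rule before baseline and does not meet [30].

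**5. Follow the person into the analysis.** Someone who passes [30] as written is correctly enrolled. The person is in the mITT population. The per-protocol definition (SAP Sections 5.3.1 and 5.8) does not remove someone who simply stops the drug and takes study doses. The primary ANCOVA adjusts for baseline UAS7 only. With 60 randomized 3:1, the arms are 60 × 3/4 = 45 and 60 × 1/4 = 15.

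**The case against.** The strongest case on the other side has four parts.

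- **Section 6.5.4 may already forbid a dose taken the day before baseline.** Screening is Period 1 of the study, so on a plain reading this is right. One might infer that the prohibition starts only on Day 1, and the text does not say that. What stands against the objection is that no interval is set, and a dose shortly before consent is untouched.
- **Other criteria may exclude such a person.** Inclusion [1] and exclusions [21] and [22] will remove some people. A reader might infer that nothing else could exclude a long-term user; that is too absolute. The gap is that none of these criteria does so reliably.
- **A narrower entry rule than on-study rule is not in itself a contradiction.** True in general. Here, though, [30] is described as serving washout, and for interval-dosed use it does not.
- **The effect is not shown to be large, or directional.** This stands in full. Randomization spreads such participants over both arms in expectation. A reader might be tempted to put a size on it through BOCF: with planned changes of 17 and 10, one participant set to zero change moves the expected difference of 7 by 17/45 = 0.38 points (LY3454738) or 10/15 = 0.67 points (placebo). Those figures describe any participant with a missing Week 12 score, whatever the cause. Stopping study drug does not by itself trigger BOCF, because comparisons are made regardless of treatment discontinuation (Section 9.1) and only missing Week 12 scores are imputed (Section 9.4.2). The documents give no count of affected people to multiply by.

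**Conclusion.** The mismatch is real. As written, [30] admits people with recent, regular exposure to methotrexate, cyclophosphamide or IV immunoglobulin at any interval of 3 days or more, while Section 6.5.4 prohibits these drugs without qualification. The conclusion rests on one assumption from outside the documents: that some candidates take these drugs at such intervals.

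The likely statistical consequence is added noise, or a chance imbalance that a placebo arm of 15 absorbs poorly, together with overlap between residual immunosuppression and the study drug. A systematic bias for or against LY3454738 is not supported. The number of people affected and the shift in the primary comparison cannot be computed from the documents, and the number may well be small. The change is worth making because it is specific and cheap.

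**What to change.** Reconcile exclusion [30] with Section 6.5.4. Amend the definition of routine use in [30] so that the entry criterion and the on-study prohibition cover the same exposures to methotrexate, cyclophosphamide and IV immunoglobulin, including regimens not dosed daily or on alternate days. In the same edit, say whether the prohibition in Section 6.5.4 begins at screening. The clinical rule and the length of the window are for the sponsor to decide.

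The cost is a short protocol amendment. A few candidates would become ineligible or would have to rescreen. Section 5.4.1 already allows one rescreening under [30] with sponsor approval.
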